9.4.4. Electrocardiograms

Descriptive statistics for ECG parameters (ie, ventricular heart rate, RR interval, PR interval, QRS interval, QT interval, and QTc) and changes from baseline values at each assessment time

point will be presented by study intervention group. The QTc is calculated using both the Bazett and Fridericia corrections.

The number and percentage of participants with PCS postbaseline ECG values will be tabulated by study intervention group. The criteria for PCS ECG values will be detailed in the SAP. The percentages will be calculated relative to the number of participants with available non-PCS baseline values and at least 1 postbaseline assessment. The numerator will be the total number of participants with available non-PCS baseline values and at least 1 PCS postbaseline value. A supportive listing of participants with PCS postbaseline values will be provided for the Safety Population.

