Sites shall transmit all study-required ECGs obtained to the ECG vendor. All ECGs performed during a given visit should be recorded on the repeating eCRF in the respective visit. Only ECGs done at unscheduled visits will be recorded as unscheduled ECGs. All readable ECGs received by the vendor shall be sent for cardiologist over-read. The sponsor will receive all ECG data,

including cardiologist over-read interpretation, in the data transfer, including those ECGs that could not be evaluated.

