9.4.3. Vital Signs

Descriptive statistics for height, weight, and vital signs (supine systolic and diastolic blood pressure, supine pulse rate, respiration rate, and temperature) at baseline and changes from baseline at each assessment timepoint will be presented by study intervention.

Vital sign values will be considered to be PCS values if they meet both the observed-value criteria and the change-from-baseline-value criteria (as defined in the SAP). The number and percentage of participants who have PCS postbaseline vital sign values will be tabulated by study intervention group. The percentages will be calculated relative to the number of participants who have available non-PCS baseline values and at least 1 postbaseline assessment. The numerator will be the total number of participants with at least 1 PCS postbaseline value. A supportive listing of participants with PCS postbaseline values will be provided for the Safety Population.

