9.5 Electrocardiogram

Descriptive statistics for ECG parameters (i.e., ventricular heart rate, RR interval, PR interval, QRS interval, QT interval, and QTc) and changes from baseline values at each assessment time point will be presented. The QTc is calculated using both the Bazett and Fridericia corrections.

ECG parameter values are considered PCS if they meet or exceed the higher-limit PCS criteria listed in Table B-3 of the [Appendix B](#). The number and percentage of participants with PCS postbaseline ECG values will be tabulated. The percentages will be calculated relative to the number of participants with available non-PCS baseline values and at least 1 postbaseline assessment. The numerator will be the total number of participants with available non-PCS baseline values and at least 1 PCS postbaseline value. A supportive listing of participants with PCS postbaseline values will be provided for the Safety Population.

In addition, a tabular display showing all AEs that occurred in participants who had postbaseline PCS ECG values will be provided.

A shift table from baseline to the end of Intervention Period in the Investigator's overall interpretation of the ECG will be presented by study intervention group for the following categories: normal; abnormal, not clinically significant; abnormal, clinically significant. A tabular display showing participants with postbaseline clinically significant ECG abnormalities according to the Investigator's overall interpretation will be provided.

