QRS interval	msec	QRS ≥ 115 msec (6-7 (inclusive) years) QRS ≥ 125 msec (8-15 (inclusive) years) QRS ≥ 150 msec (16-18 (inclusive) years)
PR interval	msec	PR > 225 msec (6-7 (inclusive) years) PR > 250 msec (8-18 (inclusive) years)
QTc(F)	msec	>480

QTc(F) = QT Corrected by Fridericia's formula

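### The ECG outlier analysis flags QTc only when QTcF is above 480 msec, and no planned output counts participants by the size of their QTc increase

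*Protocol*

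**What the plan says.** Protocol 9.4.4 plans a table of participants with PCS postbaseline ECG values and leaves the definition to the SAP: "The criteria for PCS ECG values will be detailed in the SAP".

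SAP 9.5 supplies it: "ECG parameter values are considered PCS if they meet or exceed the higher-limit PCS criteria listed in Table B-3". Table B-3 in SAP Appendix B has rows for QRS, PR and QTcF only. The QTc row is "QTc(F) msec >480", with no age bands, no change criterion and no limit for the Bazett correction. SAP 9.5 does say "The QTc is calculated using both the Bazett and Fridericia corrections".

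SAP 9.5 plans these other ECG outputs:

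- Descriptive statistics; the parameter list there ends "QT interval, and QTc) and changes from baseline values at each assessment time point will be presented".
- A listing of participants with PCS postbaseline values, and a display of the AEs in those participants. Both depend on Table B-3.
- "A shift table from baseline to the end of Intervention Period in the Investigator's overall interpretation of the ECG will be presented", together with a display of participants whose postbaseline ECG the investigator judged clinically significant.

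Under Protocol 8.2.3 the only scheduled on-treatment ECG is at the EOT Visit (Week 24 for FC, Week 52 for IBS-C). Under SAP 9.1, a participant who enrolls within 28 days of the last lead-in dose takes the lead-in study's baseline as the baseline here.

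**The concern.** Long-term safety is the study's only objective, and ECG abnormalities related to diarrhea are part of the AESI definition (Protocol 8.3.1). Protocol 2.2.4 reports severe diarrhea with hypokalemia in adults after marketing. With one scheduled on-treatment ECG per participant, the PCS table is the main categorical ECG result that does not rest on someone's judgement.

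A fixed upper limit answers whether a participant ended above 480 msec. It does not answer whether QTc rose materially on treatment. The second question could be answered from data already in hand, because change from baseline is computed for each participant with a baseline and a postbaseline ECG, but no output turns it into a count. A report of no PCS QTc values could then be read as showing no large increases, which the rule cannot show.

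A smaller point is that the text and the table disagree at the boundary. SAP 9.5 makes a value equal to the limit PCS, while Table B-3 uses a strict inequality for PR and QTcF. A QTcF of exactly 480 msec, or a PR of exactly 225 or 250 msec in the relevant age band, is PCS by one and not by the other.

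**Working it through.** There is no figure in the plan to reproduce: the sample size has no statistical basis (SAP 2.4) and nothing is tested (SAP 11.0). The check is of the rule itself.

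**Step 1. Largest rise that stays unflagged (no assumption needed).** By Table B-3, a participant is not PCS while QTcF is at or below 480, so the largest unflagged rise is 480 − baseline.

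| Baseline QTcF (msec) | 380 | 400 | 410 | 420 | 440 |
|---|---|---|---|---|---|
| Largest unflagged rise | 100 | 80 | 70 | 60 | 40 |

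A move from 400 to 475 is +75 msec and is not PCS.

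**Step 2. How often each rule flags a true rise of 70 msec (illustration).** The documents give no QTc distribution, so all inputs are assumed: a normal model, baseline mean m of 390–420 msec, and between-participant and within-participant SDs (SDb, SDw) of (15, 10), (18, 12) and (20, 15).

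- 480 rule: P = 1 − Φ((480 − m − 70) / √(SDb² + SDw²)). The total SDs are 18.03, 21.63 and 25.00.
- Change of 60 or more: P = 1 − Φ((60 − 70) / (√2 × SDw)). The SDs of change are 14.14, 16.97 and 21.21.

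| (SDb, SDw) | >480, m=390 | m=400 | m=410 | m=420 | Change ≥60, any m |
|---|---|---|---|---|---|
| (15, 10) | 13.4% | 29.0% | 50.0% | 71.0% | 76.0% |
| (18, 12) | 17.8% | 32.2% | 50.0% | 67.8% | 72.2% |
| (20, 15) | 21.2% | 34.5% | 50.0% | 65.5% | 68.1% |

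The gap is wide at 390 and nearly closes at 420.

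**Step 3. Chance flags with no true change.** P(change ≥60) = 1 − Φ(60 / (√2 × SDw)) = 0.001%, 0.02% and 0.23% for the three SD pairs. For 30 to <60, Φ(60/SD) − Φ(30/SD) with the same SDs of change gives 1.7%, 3.8% and 7.6%. The lower category is therefore noisier. Neither figure allows for drift with growth between the two ECGs.

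**Step 4. Could the PCS count be zero when rises exist?** Suppose 5 participants each rise by exactly 60 msec, with baseline SD 15 or 20 and no other noise. P(zero flags) = Φ((480 − m − 60)/SD)^5.

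| m | 390 | 400 | 410 | 420 |
|---|---|---|---|---|
| SD 15 | 0.89 | 0.62 | 0.23 | 0.03 |
| SD 20 | 0.71 | 0.42 | 0.16 | 0.03 |

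Among 120 participants, these five would move the pooled mean change by 5 × 60 / 120 = 2.5 msec. The SAP reports FC and IBS-C separately by intervention group, so the mean of a smaller group containing all five would move more. In neither case does the mean say how many participants rose.

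**The case against.** The strongest reply is that a large rise would not go unseen. QTc change is summarised under both corrections. If the minimum and maximum that SAP 7.0 names for continuous variables are also used for ECG, a +75 would appear as the maximum. Clinically significant ECG findings are AEs (Protocol Appendix 3), diarrhea-related ECG abnormalities are tabulated as AESIs (SAP 9.2.6), and clinically significant ECGs have their own display. None of these routes depends on Table B-3. That stands: the gap is in counting by size of increase, and a reader who inferred that large rises are invisible would go too far.

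Four other stronger readings are tempting, and the documents do not support them.

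- A reader might infer that the shift table rests on the investigator's unaided reading. Protocol 8.2.3 says the investigator interprets the ECG using the central report. It is true that the sponsor receives ECG data "including cardiologist over-read interpretation, in the data transfer", and that the SAP does not tabulate this over-read. But that is a separate matter and does not produce a zero PCS count.
- A reader might infer that the 480 msec limit mostly catches participants whose QTc was long at entry. SAP 9.5 restricts numerator and denominator to participants with a non-PCS baseline, so everyone counted has crossed the limit since baseline. A high baseline below 480 makes crossing easier; no more can be said.
- A reader might take the vital-sign rules as a precedent, since those values must "meet both the observed-value criteria and the change-from-baseline-value criteria". For blood pressure and pulse the change requirement narrows the flag. Only weight is flagged on change alone, and laboratory PCS uses limits without change.
- A reader might assume every participant has an ECG at entry. The schedules for enrollment within 28 days (Tables 1-1 and 1-3) contain none. Their baseline comes from lead-in protocols that are not available here.

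Two further points carry weight. The cut-offs of 30 and 60 msec are not in the documents. The study is also descriptive, with no decision rule attached to the PCS count, and Protocol 2.2.1 reports no clinically meaningful ECG differences from placebo in the adult Phase 3 studies.

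**Conclusion.** The point holds in a limited form. Table B-3 defines QTc PCS only as QTcF above 480 msec, and no planned output counts participants by size of increase. It follows by arithmetic alone that a rise such as 400 to 475 msec is missing from the PCS count, the PCS listing and the linked AE display, unless the participant qualifies on PR or QRS.

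The size of the loss is not known from the documents. Under the assumptions shown, a +70 msec rise is flagged in about 13–71% of participants by the 480 rule and about 68–76% by a 60 msec change rule. Most of the spread comes from the assumed baseline mean. If baseline QTcF averages near 420 msec, little is lost; near 390, most such rises go unflagged.

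This is a reporting weakness that the SAP should correct, not evidence that a cardiac signal would be concealed. The mismatch between SAP 9.5 and Table B-3 is a plain inconsistency that needs no assumption, though it matters only for values exactly at a limit.

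**What to change.** In SAP 9.5 and Table B-3:

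1. Add QTcF change-from-baseline categories to the ECG outlier summary as a separate analysis category, not as an extra condition on the 480 msec rule. Categories of 30 to <60 and ≥60 msec are an example; the sponsor should confirm the cut-offs. Give numbers and percentages by intervention group, and list the participants who meet them.
2. State beside the table that for participants enrolled within 28 days the baseline is the lead-in ECG, so the change spans the lead-in study as well as LIN-MD-66. For an IBS-C completer of LIN-MD-64 who finishes Week 52, that is at least 12 + 52 = 64 weeks.
3. Use one inequality for PR and QTcF in both the text of SAP 9.5 and Table B-3.
4. Optionally, tabulate or list the central cardiologist over-read beside the investigator's category.

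The cost is SAP wording, a few table rows and a listing from data already transferred; visits, eligibility and participant management are untouched. The downside is an occasional chance flag, mainly in the lower category (1.7–7.6% under the assumptions above), because a single EOT ECG is compared with a baseline that may be more than a year old in a growing child.

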9.5. Interim Analyses

An interim analysis to assess long-term safety of linaclotide may be performed after at least 120 participants have completed the study. Data will be locked after performing data cleaning. Results from the interim analysis will be described in an interim clinical study report.

10. Supporting Documentation and Operational Considerations

10.1. Appendix 1: Regulatory, Ethical, and Study Oversight Considerations

10.1.1. Regulatory and Ethical Considerations

- This study will be conducted in accordance with the protocol and with the following:
 - Consensus ethical principles derived from international guidelines including the Declaration of Helsinki and Council for International Organizations of Medical Sciences (CIOMS) International Ethical Guidelines
 - Applicable ICH/ISO Good Clinical Practice (GCP) guidelines
 - Applicable laws and regulations
- The protocol, protocol amendments, ICF, investigator's brochure, and other relevant documents (eg, advertisements) must be submitted to an IRB/IEC by the investigator and reviewed and approved by the IRB/IEC before the study is initiated.
- Any amendments to the protocol will require IRB/IEC approval before implementation of changes made to the study design, except for changes necessary to eliminate an immediate hazard to study participants.
- The investigator will be responsible for the following:
 - Providing written summaries of the status of the study to the IRB/IEC annually or more frequently in accordance with the requirements, policies, and procedures established by the IRB/IEC
 - Notifying the IRB/IEC of SAEs or other significant safety findings as required by IRB/IEC procedures
 - Providing oversight of the overall conduct of the study at the site and adherence to requirements of applicable local regulations, for example 21 CFR, ICH guidelines, the IRB/IEC, and European regulation 536/2014 for clinical studies (if applicable)

10.1.2. Financial Disclosure

Investigators and subinvestigators will provide the sponsor with sufficient, accurate financial information as requested to allow the sponsor to submit complete and accurate financial certification or disclosure statements to the appropriate regulatory authorities. Investigators are responsible for providing information on financial interests during the course of the study and for 1 year after completion of the study.

10.1.3. Informed Consent Process

Procedures will comply with 21 CFR, Parts 50 and 312. Signed informed consent will be obtained for the participant from the parent/guardian/LAR and/or the caregiver of each participant participating in a clinical research study. This consent must include the following items:

- A statement that the study involves research and an explanation of the purposes of the research; a description of the procedures to be followed and the identification of any procedures that are experimental; and the expected duration of the participant's participation
- A description of any reasonably foreseeable risks or discomforts to the participant
- A description of any benefits to the participant or to others that may reasonably be expected from the research. If the participant is to be paid for participating in the study, the consent form must state the amount that he/she will receive and the schedule of payment (to ensure neither coercion nor undue influence)
- A disclosure of appropriate alternative procedures or courses of treatment, if any, that might be advantageous to the participant
- A statement describing the extent, if any, to which confidentiality of records identifying the participant will be maintained and noting the possibility that the health authority; the sponsor, the IRB/EC; or an authorized contract research organization may inspect the records
- For research involving more than minimal risk, an explanation of whether any medical treatment is available if injury occurs and, if so, what it consists of or where further information may be obtained
- An explanation of whom to contact, including the relevant telephone number, for answers to pertinent questions about the research and the research participant's rights and whom to contact in the event of a research-related injury to the participant. (Note: In some cases, it may be necessary to identify a person other than the investigator as the contact. The guidance of the IRB/EC may be required)
- A statement that participation is voluntary, that refusal to participate will involve no penalty or loss of benefits to which the participant is otherwise entitled, and that the participant may discontinue participation at any time without penalty or loss of benefits to which the participant is otherwise entitled
- A statement that the particular treatment or procedures may involve risks to the participant (or to the embryo or fetus if the participant is, or may become, pregnant) that are at present unforeseeable

- The expected circumstances for which the participant's participation may be terminated by the investigator without regard to the participant's consent
- Any additional costs to the participant that may result from participation in the research
- The consequences of a participant's decision to withdraw from the research and procedures for an orderly termination of the participant's participation
- A statement that significant new findings developed during the course of the research that may relate to the participant's willingness to continue participation will be provided to the participant
- The approximate number of participants involved in the study
- A statement of consent (eg, "I agree to allow (my child) to participate . . .")
- A place for the participant's parent/guardian/LAR signature and date of signing
- A statement indicating that information about this study has been, or will be, entered into a databank that is publicly accessible at www.ClinicalTrials.gov.

A copy of the signed consent form must be given to the participant's parent/guardian/LAR.

Signed informed consent will be obtained from caregiver of a participant and will include a statement agreeing to participate in the study.

In addition, the participant will be asked to provide assent that will include a statement agreeing to participate in the study.

10.1.4. Data Protection

- Participants will be assigned a unique identifier. Any participant records or datasets that are transferred to the sponsor will contain the identifier only; participant names or any information which would make the participant identifiable will not be transferred.
- The participant must be informed that his/her personal study-related data will be used by the sponsor in accordance with local data protection law. The level of disclosure must also be explained to the participant.
- The participant must be informed that his/her medical records may be examined by Clinical Quality Assurance auditors or other authorized personnel appointed by the sponsor, by appropriate IRB/IEC members, and by inspectors from regulatory authorities.

10.1.5. Posting Clinical Study Data

All data generated in this study are the property of the sponsor. An integrated clinical and statistical report will be prepared at the completion of the study.

10.1.6. Data Quality Assurance

- All participant data relating to the study will be recorded on printed or eCRFs unless transmitted to the sponsor or designee electronically (eg, laboratory data). The investigator is responsible for verifying that data entries are accurate and correct by physically or electronically signing the eCRF.
- The investigator must maintain accurate documentation (source data) that supports the information entered in the eCRF.
- The investigator must permit study-related monitoring, audits, IRB/IEC review, and regulatory agency inspections and provide direct access to source data documents.
- The sponsor or designee is responsible for the data management of this study including quality checking of the data.
- Study monitors will perform ongoing source data verification to confirm that data entered into the eCRF by authorized site personnel are accurate, complete, and verifiable from source documents; that the safety and rights of participants are being protected; and that the study is being conducted in accordance with the currently approved protocol and any other study agreements, ICH GCP, and all applicable regulatory requirements.
- Records and documents, including signed ICFs, pertaining to the conduct of this study must be retained by the investigator for 15 years after study completion unless local regulations or institutional policies require a longer retention period. No records may be destroyed during the retention period without the written approval of the sponsor. No records may be transferred to another location or party without written notification to the sponsor.

10.1.6.1. Data Monitoring

Before any participant enters the study, a representative of the sponsor will meet with the investigator and the study site staff to review the procedures to be followed during the study. Electronic data capture (EDC) functionality training is provided via computer-based training to train investigators and authorized designees on recording the data in the eCRFs using the EDC system. After the first participant is enrolled, the sponsor's representative, a Regional Site Manager or designee, will periodically monitor the progress of the study by conducting on-site visits. This Regional Site Manager or designee will review query statuses remotely, possibly warranting more frequent communication and/or site visits with the investigator and the study

site staff. The investigator will make available to the Regional Site Manager or designee source documents (written notes and electronic medical records, if used), signed consent forms, and all other study-related documents. The investigator and the study site staff will be responsible for data entry of participant data into the eCRFs via the EDC system, resolving data queries generated via the EDC system and providing missing or corrected data. The investigator or designee will be responsible for approving all changes performed on the data and endorsing the participant data within the EDC system. This approval method will include applying an electronic signature linked to a uniquely assigned username and password that together will represent a traditional handwritten signature used in the past.

